#### 9.2.4. Coding of adverse events, concomitant medications, etc.

AEs and medical history will be coded using the Medical Dictionary for Regulatory Activities (MedDRA) version 18.0 or later (the exact version to be determined when coding is done). Coding will be to the level of the lowest level term (LLT). Concomitant medications and pre-treatment CAH medications will be coded using the World Health Organisation (WHO) Drug Dictionary including Anatomical Therapeutic Chemical (ATC) drug classification.

### 9.3. Assessment time windows

#### 9.3.1. Definition of permissible time windows

Actual study day will be calculated by:

- Date of assessment - Date of randomisation + 1

Participants will receive their first dose of randomised treatment in the evening of the second baseline visit (Day 2 of Visit 1) after they have been randomised. As such study day 1 will be considered the day of randomisation. All assessments which are performed at the baseline visit (Visit 1, Days 1 and 2) will be considered prior to randomised study treatment.

All assessments that are summarised by visit (endocrine profile, DEXA, ECG, laboratory results, Vitals etc.) will be summarised according to the scheduled visit. Any extreme deviations between the actual study day of the scheduled visit and the target study day (see Table 6) will be discussed at the Data Review Meeting. A deviation will be considered extreme if more than +/- 3 weeks from visit 2, or +/- 4 weeks from visit 3 or 4.

*Table 6: Target study day for visit assessments*

Visit number	Visit description	Target study day	Target study day range
Visit 0	Screening		<-1
Visit 1	Baseline	-1,1	
Visit 2	Week 4	29,30	>8 to <51
Visit 3	Week 12	85,86	>57 to <114
Visit 4	Week 24	169,170	>141 to <198

*Note: There is no study day 0 as per CDISC standards. Study day 1 is first day of dosing.*

#### 9.3.2. Baseline Assessment

Baseline, used in calculations for change from baseline summaries, will be defined as the latest pre-dose measurement. This is expected to be the visit 1 assessment, however if a result is missing and there is a suitable result available at the screening visit (taking account of fasting requirements where needed), this will be used in its place.

#### 9.3.3. Methods for handling out-of-window observations

Missing 17-OHP and A4 values will be handled as follows:

- If the Day 1 15:00 sample of a 24-hour profile is completely missing, the result from the 17:00 planned time point will be used.
- If the Day 2 15:00 sample of a 24-hour profile is completely missing, the result from the 13:00 planned time point will be used.

- For all other time points where the result is completely missing, the average of the two closest results will be calculated and used for the missing time point.
- If the result at any time point is below the lower limit of quantification (LLOQ), a value of half the LLOQ will be substituted.
- For the purpose of analysis, a result will be considered to be out-of-window if more than +/-60 minutes from the scheduled time point. For each time point where the result is 'out-of-window':
  - If the out-of-window result is >60 minutes after the scheduled time point then the average of the previous scheduled time point and the out-of-window result will be calculated and used for the scheduled time point with the out-of-window result.
  - If the out-of-window result is >60 minutes before the scheduled time point then the average of the next scheduled time point and the out-of-window result will be calculated and used for the scheduled time point with the out-of-window result.

Subjects with 2 or more of the expected results missing (or outside of a +/-15 minute window) for a particular 24hr period were discussed on a case-by-case basis at the Data Review Meeting which occurred prior to database lock and study unblinding.

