### **13.1.4 Missing Outcome Data**

Missing 17-OHP and A4 values (including those considered missing due to being taken outside the permitted time window) within the 24-hour hormone profile will be imputed by linear interpolation of the two closest non-missing measurements to the scheduled missing time point (including out-of-window measurements). In the event that several values are missing from a single profile, a decision will be made about the validity of the whole profile will be made at the Data Review Meeting on a case-by-case basis (see Section 13.10)

Subjects who withdraw from the study will be assessed on the basis of the latest available 24-hour profile. This is a conservative procedure as subjects enter the study already receiving a suitable dose of their standard therapy.

Exploratory and sensitivity analyses will be performed to assess the effect of any missing data on the efficacy conclusions.

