## 9. Data handling conventions

### 9.1. Premature withdrawal and missing data

Missing 17-OHP and A4 values (including those considered missing due to being taken outside the permitted time window) within the 24-hour hormone profile will be imputed by linear interpolation of the two closest non-missing measurements to the scheduled missing time point (including out-of-window measurements). Further details are given in Section 9.3.3. In the event that several values are missing from a single profile, a decision will be made about the validity of the whole profile at the Data Review Meeting on a case-by-case basis.

For efficacy analyses based on the Week 12 and Week 24 visits, subjects who have withdrawn from the study will be assessed on the basis of the latest available 24-hour profile. This is a conservative procedure as subjects enter the study already receiving a suitable dose of their standard therapy.

When calculations must be based upon incomplete dates the following process will be used. If year is missing do not impute. The value should be considered missing. If year is populated but both month and day are missing then the date defaults to 1st July. If day only is missing then the day defaults to the 15th of the month.

For adverse events and concomitant medications, if year is missing do not impute. If start year is populated but both month and day are missing, or if month is missing and day is present, then the date defaults to 1st January. If day only is missing then the day defaults to the 1st of the month. If end year is populated but both month and day are missing, or if month is missing and day is present, then the date defaults to 31st December. If day only is missing then the day defaults to last day of the month. For definition of treatment emergent and ongoing, if partial dates are only available for start and end, then we are conservative and assume treatment emergent/ongoing.

For those subjects with one middle dose then this is considered as “middle 1”, and middle2 is blank for all subjects except those with a second middle dose.

Exploratory and sensitivity analyses will be performed to assess the effect of any missing data on the efficacy conclusions. This will be discussed at the Data Review Meeting and a decision will be made on the appropriate analyses.

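### SAP 9.3.3 fills missing and out-of-window hormone samples with an unweighted average, contradicting the linear interpolation in Protocol 13.1.4 and SAP 9.1; the primary effect is small, but a 09:00 responder can be reclassified

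*SAP*

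**What the plan says.** Protocol 13.1.4 says that missing profile values, including those treated as missing because they were out of window, "will be imputed by linear interpolation of the two closest non-missing measurements to the scheduled missing time point", and out-of-window measurements may serve as one of the two. SAP 9.1 repeats this and adds: "Further details are given in Section 9.3.3".

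SAP 9.3.3 then gives different arithmetic:

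- Interior sample completely missing: "the average of the two closest results will be calculated and used for the missing time point".
- Sample too late: "the average of the previous scheduled time point and the out-of-window result will be calculated".
- Sample too early: "the average of the next scheduled time point and the out-of-window result will be calculated".
- Definition of the window: "a result will be considered to be out-of-window if more than +/-60 minutes from the scheduled time point".
- Day 1 or Day 2 15:00 sample completely missing: the 17:00 or the 13:00 result, respectively, is used.

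Profiles with two or more results missing or outside ±15 minutes went to case-by-case discussion at the Data Review Meeting. Protocol 13 allows minor changes of method if they are documented in the SAP and the study report. SAP Section 12 lists changes to shift tables and to dose-level splits, and nothing on imputation. The SAP version 4.0 revision entry for 9.3.3 covers the wider window and the rule for a missing 15:00 sample.

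**The concern.** Linear interpolation weights each neighbour by its distance from the scheduled time; a plain average does not. A programmer working from SAP 9.1 and one working from 9.3.3 would derive different values from the same samples, and nothing in the SAP says which section governs.

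The filled values enter the primary variable (SAP 9.2.2), where one point carries a weight of 1/12. They also enter the 09:00 responder analysis (SAP 10.6.1), where one concentration settles the outcome and nothing dilutes an error. A single out-of-window 09:00 sample does not reach the Data Review Meeting threshold of two.

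**Working it through.** **Inputs from the documents.** Thirteen samples two hours apart (Protocol 11.1.2). Analysis window ±60 minutes (SAP 9.3.3). 17-OHP responder range 1.2–36.4 nmol/L (SAP Table 7). Planned difference 0.78 − 0.20 = 0.58 in log mean SDS (SAP 5). Male 17-OHP limits 1.2 and 6.7 nmol/L (SAP Table 2).

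**Assumed.** All concentrations below are illustrative, since the documents give no profile data. Neighbouring samples are taken to be on schedule.

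**Plan's own figures.** For males, the midpoint is (ln 1.2 + ln 6.7)/2 = 1.042 and the SD is (ln 6.7 − ln 1.2)/4 = 0.430. Both match SAP Table 3. The plan gives no figure for the imputation rule itself.

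**1. One isolated missing interior sample.** The neighbours are two hours either side, so interpolation weights are ½ and ½. Neighbours of 5 and 50 give 27.5 under both rules.

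**2. Sample d minutes late.** Interpolating to the scheduled time gives the previous point weight d/(120 + d). SAP 9.3.3 always gives it 0.5.

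| d (min) | Interpolation weight on previous point | SAP 9.3.3 |
|---|---|---|
| 61 | 61/181 = 0.337 | 0.5 |
| 75 | 75/195 = 0.385 | 0.5 |
| 90 | 90/210 = 0.429 | 0.5 |
| 119 | 119/239 = 0.498 | 0.5 |

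The discrepancy is largest just outside the window and has almost gone by two hours. Early samples mirror this, with the next point in place of the previous one.

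**3. Responder example.** 07:00 = 80; 09:00 sample 65 minutes late = 6.

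- SAP 9.3.3: (80 + 6)/2 = 43.0, above 36.4, non-responder.
- Interpolation: 80 − 74 × 120/185 = 32.0, within range, responder.
- Limits of the flip: 80 − 74 × 120/(120 + d) ≤ 36.4 requires d ≤ 120 × 74/43.6 − 120 = 83.7 minutes. At 90 minutes interpolation gives 80 − 74 × 120/210 = 37.7, and both rules give a non-responder.

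**4. The same point in the primary variable (male).** ln(43/32)/0.430 = 0.69 SDS at that time point, and 0.69/12 ≈ 0.06 on the subject's mean SDS. On an assumed mean SDS of 4.04 that is ln(4.101/4.044) = 0.014 on the log scale. One such subject in an arm of 51 (102/2, equal allocation assumed) moves the arm mean by about 0.014/51 = 0.0003.

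**5. Two consecutive missing samples.** With flanking values 10 and 80, interpolation gives 33.3 and 56.7. Averaging the flanking values gives 45 and 45. In the male score the two errors are +0.70 and −0.54 SDS and largely cancel: (0.70 − 0.54)/12 ≈ 0.013 on the mean SDS. In an assumed male profile of 10, 8, 6, 5, 5, 8, 20, 60, 120, 60, 25, 15, 10 nmol/L from 15:00 to 15:00, the rules differ by 0.001 to 0.010 in log mean SDS for runs of two or three missing samples.

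Those figures take the two closest results to be the flanking ones, which the text does not say. If 03:00 and 05:00 are missing, then 23:00 and 07:00 are both four hours from 03:00. In this profile 03:00 becomes (8 + 120)/2 = 64 if 07:00 is chosen, or (8 + 5)/2 = 6.5 if 23:00 is. Breaking both ties one-sidedly (6.5 at 03:00 and (120 + 60)/2 = 90 at 05:00) moves log mean SDS by 0.09 from the interpolated result.

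**6. Profile ends.** A Day 1 15:00 sample taken after 16:00 has no earlier scheduled point, and a Day 2 15:00 sample taken before 14:00 has no later one. SAP 9.3.3 gives no value in these two cases.

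**The case against.** The best defence is that this is a small drafting inconsistency. SAP 9.1 still states interpolation, the rules coincide in the simplest case, sites work to ±10 minutes, and no frequency of deviations beyond 60 minutes is given. Profiles with several missing values went to masked review, which could reject a whole profile. The responder flip uses chosen values and a narrow range of delays. All of this stands and limits the size of the point. It does not remove the contradiction, and review does not reach a lone late 09:00 sample.

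A reader might infer three stronger things that the documents do not support:

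- *That 9.3.3 fails at the profile ends generally.* Completely missing 15:00 samples have their own rules. Only the two out-of-window cases in step 6 are undefined.
- *That the SAP has replaced the protocol rule.* SAP 9.1 keeps it, so the SAP disagrees with itself as well as with the protocol.
- *That averaging raw concentrations is an error because the SDS is computed on logs.* Protocol 13.1.4 and SAP 9.1 also interpolate the values without naming a log scale, and SAP 9.2.2 takes the logarithm afterwards. Log-linear interpolation would give 14.9 in the step 3 example, 2.5 SDS from 43.0, but that compares 9.3.3 with a method neither document specifies.

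**Conclusion.** The contradiction is real and worth correcting. SAP 9.3.3 conflicts with Protocol 13.1.4 and SAP 9.1 for samples more than 60 minutes off schedule and for consecutive gaps. It is ambiguous about which results are closest, it leaves two end cases undefined, and Section 12 does not declare the difference.

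It would be wrong to conclude that the primary result is in doubt. In the cases worked, the shift for one subject is about 0.06 in mean SDS for one late sample, and at most about 0.01 in log mean SDS for consecutive gaps filled from flanking values. The largest, 0.09, needs an unlikely reading of the tie, in a profile that would have gone to review. The planned difference is 0.58. The practical exposure is misclassification of individual 09:00 responders. How many subjects are affected cannot be judged from the documents.

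**What to change.** In SAP 9.3.3, replace the simple averages with time-weighted linear interpolation to the scheduled time, between the nearest observed samples before and after it, using recorded sampling times. This restores the rule in Protocol 13.1.4 and SAP 9.1 and removes the tie. For the two undefined end cases, carry the out-of-window 15:00 value itself. Interpolating between it and its only neighbour would in fact be extrapolation, because both lie on the same side of 15:00. State in 9.1 and 9.3.3 which scale is used, and list any remaining departure from the protocol in Section 12. Log-scale interpolation is optional and could be a sensitivity analysis.

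The cost is a few sentences in the SAP and a few lines of code. Exact sampling times are already recorded in the eCRF (Protocol Table 1 notes and 11.2), so no new data are needed.

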#### **9.3.4. Other clinical laboratory values below the lower limit of quantification**

If a clinical laboratory result is below the LLOQ at any time point, a value equal to the LLOQ will be substituted.

### **9.4. Handling outliers**

Any extreme values which are considered to have potential to impact the interpretation of results will be discussed at the Data Review Meeting (See 4.1) and sensitivity analyses may be performed as required.

## **10. Study population**

### **10.1. Disposition of subjects**

Subject disposition will be listed and summarised by treatment group (including screen failures) and pre-baseline standard therapy. The summary will include reason for withdrawal and whether the subject is continuing into the extension study.

### **10.2. Protocol deviations**

Any deviations from the protocol will be reviewed at the Data Review Meeting following trial completion but prior to database lock. Each protocol deviation will be classified as either 'minor' (unlikely to affect trial outcomes) or 'major' (likely to affect outcomes). Any subject considered to have a major protocol deviation will be excluded from the Efficacy Analysis set (See 6.223). In addition, protocol deviations will be grouped into the following high-level categories:

- Inclusion criteria – subject failed to meet all inclusion criteria,
- Exclusion criteria – subject met at least one exclusion criteria,

---

 This differs from the +/- 10 minute window specified for investigators in the protocol so that results within a wider window can be considered acceptable for analysis.

- Study procedure – site or subject did not follow procedures specified in protocol,
- Titration – site or subject deviated from the titration process,
- Treatment – IMP not taken as per protocol,
- Local sampling – site performed endocrine sampling locally.

Protocol deviations will be listed and summarised by randomised treatment group, classification (major or minor) and protocol deviation category.

### 10.3. Demographic and baseline characteristics

The following demographic and baseline characteristics will be summarised and listed at the screening visit: age (calculated in whole years), gender, race, ethnicity, height, weight, BMI, waist circumference. Age will be split into four groups and will be included in the demographic and baseline characteristics summary table. The following age groups will be displayed:

- $\geq 18$  -  $< 30$
- $\geq 30$  -  $< 50$
- $\geq 50$  -  $< 70$
- $\geq 70$

Baseline disease characteristics including time since CAH diagnosis, whether the subject was hospitalized in the last year due to CAH, the number of adrenal crises in the past year and prior CAH medications will be summarised and detailed listings will be produced.

Congenital adrenal hyperplasia medical history, other medical history excluding CAH related events and prior medications will each be summarised and detailed listings will be produced. Mutation status will also be listed.

### 10.4. Treatment compliance

For treatment compliance, overall compliance will be calculated and the overall period will start from the first dose of randomised study treatment up to the last dose taken.

The overall compliance will be calculated as a percentage for each subject by

$$\frac{\text{actual total dose}}{\text{expected total dose}} \times 100.$$

To calculate the expected total dose, dose titrations are to be taken into account. For each dose regimen the expected total dose will be calculated by summing the total daily dose for the duration of the dose regimen. If a subject has their dose changed then the expected total dose will be calculated by summing the total daily dose of all the dosing regimens. If the study end day of a dosing regimen overlaps with the study start day of the next dosing dose regimen then the average total daily dose of the two dosing intervals will be used for the overlapping study day.

The actual total dose will be calculated by subtracting the number and dose of capsules returned from the number and dose of capsules dispensed.

Actual total dose and expected total dose will only be calculated when a subject has a full record of drug accountability.

Summary statistics will be produced for the overall subject compliance. A listing of subject compliance (including flags for when this is <80% or >120%) and a listing of drug accountability will be produced.

A listing of dispensed sick day medication accountability will be produced detailing the quantity dispensed and returned.

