### 10.2.4 Accountability

Subjects randomised to Chronocort® will return treatment pack 1 to the study team at Visit 2, treatment pack 2 to the study team at Visit 3 and treatment pack 3 to the study team at Visit 4. The study team will count the number of capsules remaining at each of these visits and enter the information in the eCRF, so compliance can be calculated against the treatment and titration prescriptions. At Visits 2 and 3 the study team will transfer empty treatment packs to the returns pharmacy at the site. At Visit 4 the study team will transfer all supplies returned by the subject to the returns pharmacy at the site. All used and unused Chronocort® will be stored at the returns pharmacy and made available for review by the Clinical Research Associate (CRA) as outlined in Section 14.8. Following the sponsor's approval, all remaining Chronocort® will either be returned to the supplier or destroyed on site within 8 weeks of completion of the study unless otherwise instructed. If a subject is continuing on the follow-on study, they will be consented for this study and undergo the relevant procedures for the first visit and then a separate treatment pack that will provide sufficient capsules to last until the next visit will be dispensed.

Dispensing of the comparator treatment will be in accordance with the site's usual procedure, but used and unused medication must be returned to the study site at each visit and

accountability conducted along similar lines to that detailed above for Chronocort®. Accountability must also be performed at each visit for the safety pack, which should be used in conjunction with the sites “sick day rules”. Any use of the medications in the safety pack should be recorded in the eCRF, along with the reason for use.

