### 2.4.1. Exploratory objectives

- To assess the efficacy of Chronocort® with regard to the effect on testosterone levels over the 6-month treatment period.
- To assess the impact of Chronocort® on cardiovascular (CV) risk (evaluated using high-sensitivity C-reactive protein [hsCRP]).
- To assess the impact of Chronocort® on bone markers of serum C-terminal cross-linked telopeptide (CTX type I) and osteocalcin (after fasting).
- To assess changes from baseline in glucose and insulin in the morning (after fasting)
- To assess changes from baseline in glycated haemoglobin (HbA1c)
- To assess changes from baseline in plasma renin activity (PRA) in the morning.

- To assess the impact of Chronocort® on quality of life (QoL) using SF-36®, Multidimensional Assessment of Fatigue (MAF), and EQ-5D™.
- To assess subject compliance in subjects treated with Chronocort® over a 6-month period.

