### 8.1. Standard summary statistics

The standard summary statistics for continuous baseline and outcome variables are: N, mean, standard deviation (SD), median, quartiles, minimum and maximum. The standard summary statistics for categorical baseline and outcome variables are: count and proportion (expressed as percentage). Geometric mean and coefficient of variation will also be presented for variables which will subsequently be log-transformed during the analysis.

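### Compliance is derived only for subjects with a full accountability record, so one missing pack count discards valid visit counts and may bias an exploratory summary

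*SAP*

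**What the plan says.** Compliance is an exploratory objective, worded for the Chronocort arm: "To assess subject compliance in subjects treated with Chronocort® over a 6-month period" (SAP 2.4.1; Protocol 6.3 has the same objective).

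The derivation is in SAP 10.4. Compliance is actual total dose over expected total dose, as a percentage, for one overall period: "the overall period will start from the first dose of randomised study treatment up to the last dose taken". The numerator is pack-based: "The actual total dose will be calculated by subtracting the number and dose of capsules returned from the number and dose of capsules dispensed". The restriction follows: "Actual total dose and expected total dose will only be calculated when a subject has a full record of drug accountability". The SAP does not define a full record, and it gives no rule for a partial one.

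The outputs in the same section are a descriptive table of the overall value and two listings, specified thus: "A listing of subject compliance (including flags for when this is <80% or >120%) and a listing of drug accountability will be produced".

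The protocol collects the data pack by pack. Section 10.2.4 has Chronocort packs 1, 2 and 3 returned at Visits 2, 3 and 4, and then: "The study team will count the number of capsules remaining at each of these visits and enter the information in the eCRF". Sections 11.1.3, 11.1.6 and 11.1.9 repeat the return and count at each visit for both arms.

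**The concern.** The rule works on the whole subject, while the data come by interval. A subject whose packs were counted at Visits 2 and 3 but whose last pack never came back has two usable counts and no compliance value. That subject is absent from the summary and cannot be flagged.

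Whether this biases the summary depends on why records are incomplete. It is plausible that a subject who does not bring a pack back also took fewer doses. Early withdrawal is one route: Protocol 11.1.9 asks only that as many Visit 4 assessments as possible be completed when a subject discontinues, so the final count is the one most at risk. If that is the pattern, the subjects who are summarised are the better compliers and the exploratory objective gets a favourable answer.

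At stake is the description of compliance, not the efficacy conclusion. The protocol's overview of Chronocort does list poor compliance among the failings of existing therapy, so the figure is likely to be read.

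**Working it through.** The documents state no compliance figure, so there is none to reproduce. Three checks can be made.

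**1. Size of the bias.** Let m be the share of subjects without a full record, C_obs the mean compliance of those with one, and C_ex the true mean compliance of those without. The all-subject mean is (1 − m) × C_obs + m × C_ex, so the overstatement is m × (C_obs − C_ex). None of the three inputs is in the documents. Assume C_obs = 95%, m from 5% to 30%, and C_ex from 50% to 100%. Overstatement in percentage points:

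| Share excluded | C_ex 100% | 95% | 85% | 75% | 50% |
|---|---|---|---|---|---|
| 5% | −0.25 | 0 | +0.5 | +1.0 | +2.25 |
| 10% | −0.5 | 0 | +1.0 | +2.0 | +4.5 |
| 20% | −1.0 | 0 | +2.0 | +4.0 | +9.0 |
| 30% | −1.5 | 0 | +3.0 | +6.0 | +13.5 |

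Example: with 20% excluded and C_ex = 75%, the all-subject mean is 0.8 × 95 + 0.2 × 75 = 91%, against a reported 95%.

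**2. What the rule prevents.** Protocol 10.2.2 puts 100 capsules each of 5, 10 and 20 mg in treatment pack 1: 100 × (5 + 10 + 20) = 3500 mg. At 30 mg a day, the protocol's maximum starting dose, 28 days require 28 × 30 = 840 mg. If pack 1 were not returned and the dispensed-minus-returned formula were applied anyway, compliance for that interval would be 3500 / 840 = 417%. Over 168 days at the same dose, with the rest taken perfectly, it would be (168 × 30 − 840 + 3500) / (168 × 30) = 7700 / 5040 = 152.8%. At lower doses it would be higher. Applying the formula to incomplete records would therefore do more harm than excluding them.

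**3. What could be recovered.** The target study days in SAP Table 6 (1, 29, 85, 169) give intervals of 28, 56 and 84 days, 168 in total.
- Only the final pack is uncounted: the first two intervals remain usable, (28 + 56) / 168 = 50% of the period.
- Pack 2 is not returned: only the first interval is secure, 28 / 168 = 17%, because capsules from pack 2 could have been taken after Visit 3.
- Pack 1 is not returned: no interval is secure, for the same reason.

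The recovery is real but partial. It is largest when only the final pack is missing, which is the early-withdrawal case.

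**The case against.** The strongest reply is that the rule is protective. An unreturned pack counted as taken gives absurd values (check 2), and restricting to full records avoids that. This stands. The protection should be kept, but it can be applied to the interval instead of the whole subject.

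The second reply is that the exclusions are visible. SAP 8.1 says: "The standard summary statistics for continuous baseline and outcome variables are: N, mean, standard deviation (SD), median, quartiles, minimum and maximum". The compliance table is planned on the safety analysis set, so the number without a value follows by subtraction, and the accountability listing shows who they are. SAP 10.2 summarises deviations, including study drug not taken as the protocol requires. SAP 11.1 summarises interruptions and the days on which drug was actually taken. None of these is limited to subjects with full accountability. A reader might infer that the compliance mean is the only evidence, or that the plan hides under-dosing. These outputs show otherwise. What the SAP lacks is a stated count by arm, with reasons.

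Third, withdrawal does not of itself lower compliance, because the period ends at the last dose taken. Protocol 11.4 asks for all efforts to complete the end-of-study assessments, and these include the pack count. This weakens the early-withdrawal route without closing it.

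Fourth, interval-based compliance does not cure the selection, because the intervals with missing returns may be the poor ones. That is correct and limits what the change can claim.

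Lastly, the SAP revision history records the choice of overall compliance alone as a deliberate decision. That decision does not explain why partial records should be unused.

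**Conclusion.** The point holds as a minor improvement. The rule drops subjects with incomplete accountability and the valid counts they do have, and the SAP neither defines the condition nor tabulates who is lost and why. That one missing count removes the subject is a reading of an undefined term, though the natural one.

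A reader might go further and infer that reported compliance is likely to be too high. The documents do not support that. They do not say how many records are incomplete, why, or how those subjects took their medication, and a count can be missing for site or dispensing reasons. The conclusion is conditional. Under the assumed inputs, with 5% to 30% excluded and a shortfall of 10 to 45 points, the overstatement runs from 0.5 to 13.5 points. It is zero if the excluded comply equally. If they took everything, it is between −0.25 and −1.5 points.

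Compliance is exploratory and descriptive. The primary analysis and the sample size do not depend on it.

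**What to change.** In SAP 10.4:

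1. Define a full accountability record.
2. Define subject compliance as the sum of actual dose over the sum of expected dose across the dispensing intervals (Visits 1–2, 2–3, 3–4) that have a known opening stock and a complete closing count. Supplies the subject keeps at a visit count as opening stock for the next interval; this matters because Protocol 10.2.4 sends only empty packs to the returns pharmacy at Visits 2 and 3.
3. Never count an unreturned pack as taken, and leave out any interval in which an uncounted earlier pack could still have been used.
4. Report by arm the number of subjects with full, partial and no accountability, with reasons.
5. Keep the full-record result as a sensitivity summary.

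The cost is SAP wording and minor programming on data already collected. The downside is that compliance covers a shorter period for some subjects. Intervals without a count also remain unobserved, so the selection is reduced and made visible but not removed.
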